### 4.2 Study Endpoints

#### 4.2.1 Phase 2

##### 4.2.1.1 Primary Endpoint

- Safety (e.g., frequency, intensity, and relationship to study drug of serious adverse events [including unexpected deaths], change from baseline in vital sign and laboratory assessments) at Day 29

CONFIDENTIAL

This material is the property of the NYU School of Medicine and Langone Medical Center. Do not disclose or use except as authorized in writing by the study sponsor

## 4.2.2 Phase 3

### 4.2.2.1 Primary Efficacy Endpoint

- Proportion of subjects recovered (defined as alive, free of respiratory failure [e.g., need for non-invasive or invasive mechanical ventilation, high flow oxygen, or ECMO], and free of renal replacement therapy [RRT]) at Day 29.

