## 4 Study Design and Endpoints

### 4.1 Description of Study Design

This multi-center, double-blind, placebo-controlled, randomized Phase 2/3 trial will study the safety, tolerability, and efficacy of bardoxolone methyl in patients hospitalized with confirmed COVID-19. Phase 2 is designed to provide an early interim analysis for safety and will enroll approximately 40 patients. Phase 3 is designed to determine whether bardoxolone methyl increases the probability of recovery at Day 29 compared with matching placebo. In phase 3, approximately 360-400 additional patients will be enrolled.

Patients will be randomized using permuted block randomization in a 1:1 fashion to either once-daily administration of bardoxolone methyl (20 mg) or matching placebo. Randomization will be stratified by study center and invasive mechanical ventilation (i.e., mechanical ventilation with endotracheal intubation) use at baseline (yes or no).

Enrollment of patients  $\geq 70$  years of age may be limited (e.g., comprise no more than 10% of all randomized patients), pending safety review by the DSMB and executive committee. Treatment will be administered for the duration of hospitalization (until recovery), with an expected duration of 10 days. For patients who are still hospitalized for more than 10 days, treatment can be continued for a maximum treatment duration of 29 days. Dose de-escalation (down to 10 mg) is permitted during the study if indicated clinically, and subsequent dose re-escalation is also permitted. Once a patient's dose has been reduced, dose re-escalation back to a higher dose is permitted.

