### 4.2.2.2 Secondday Efficacy Endpoint (assessed at Day 29 unless stated otherwise)

- Number of renal replacement therapy (RRT)-free days
- Number of mechanical ventilation-free days
- All-cause mortality
- Proportion of subjects experiencing a deterioration from baseline (as defined by a 1-point worsening) to end of treatment or Day 29 (whichever comes first) in clinical status using an 11-category ordinal scale:
  - 0 – Uninfected; no viral RNA detected
  - 1 – Asymptomatic; viral RNA detected
  - 2 – Symptomatic; Independent
  - 3 – Symptomatic; assistance needed
  - 4 – Hospitalized; no oxygen therapy
  - 5 – Hospitalized; oxygen by mask or nasal prongs
  - 6 – Hospitalized; oxygen by NIV or High flow
  - 7 – Intubation & Mechanical ventilation;  $pO_2/FIO_2 \geq 150$  or  $SpO_2/FIO_2 \geq 200$
  - 8 – Mechanical ventilation  $pO_2/FIO_2 < 150$  ( $SpO_2/FIO_2 < 200$ ) or vasopressors
  - 9 – Mechanical ventilation  $pO_2/FIO_2 < 150$  and vasopressors, dialysis or ECMO
  - 10 – Death

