## 5 Study Enrollment and Withdrawal

### 5.1 Inclusion Criteria

In order to be eligible to participate in this study, an individual must meet all of the following criteria:

1. Laboratory-confirmed COVID-19 infection as determined by polymerase chain reaction (PCR)
2. Hospitalized patients that meets one of the following conditions:
  - a. Radiographic infiltrates by imaging (chest x-ray, CT scan, etc.); OR

CONFIDENTIAL

This material is the property of the NYU School of Medicine and Langone Medical Center. Do not disclose or use except as authorized in writing by the study sponsor

- b. At rest, blood oxygen saturation  $\leq$  94%; OR
  - c. Require supplemental oxygen; OR
  - d. Requiring non-invasive ventilation; OR
  - e. Requiring invasive mechanical ventilation for up to 2 days.
3. Age  $\geq$  18 years. Enrollment of patients  $\geq$ 70 years of age may be limited (e.g., comprise no more than 10% of all randomized patients), pending safety review by the DSMB and executive committee
  4. Participant or legally authorized representative is willing to give informed consent

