### **10.4.2 Analysis of the Phase 3 Primary Efficacy Endpoint**

The primary efficacy endpoint is recovery, where recovery is defined as meeting all of the following criteria at Day 29:

- Alive,
- Free of respiratory failure, and
- Free of renal replacement therapy (RRT).

Analysis of the Phase 3 primary endpoint will occur after the last patient enrolled has been followed up to Day 29 and the study is complete. The analysis will be based on the test of treatment effect estimated from a generalized linear model analysis accounting for the stratification factors of study center and mechanical ventilation status as covariates. The primary efficacy endpoint will be a covariate-adjusted estimate as specified in the Statistical Analysis Plan. Events will be analyzed and presented as summary tables of proportion recovered with risk differences and 95% confidence intervals (CIs) for the comparison of

CONFIDENTIAL

This material is the property of the NYU School of Medicine and Langone Medical Center. Do not disclose or use except as authorized in writing by the study sponsor

bardoxolone methyl to placebo. The SAP will include additional detail of the planned analyses and definitions of sensitivity analyses.

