## **10.6 Measures to Minimize Bias**

### **10.6.1 Enrollment/Randomization/Masking Procedures**

An IWRS will be utilized to randomize patients 1:1 to once daily administration of bardoxolone methyl or placebo. Randomization will be performed using block randomization with the following strata: center and invasive mechanical ventilation (i.e., mechanical ventilation with endotracheal intubation) at baseline (yes or no). Enrollment of patients  $\geq 70$  years of age may be limited (e.g., comprise no more than 10% of all randomized patients), pending safety review by the DSMB and executive committee

All patients, investigators, site personnel, laboratories, and study personnel with direct involvement in the conduct of the study or their designees will be blinded to treatment assignments. To prevent potential bias, appropriate measures will be taken to ensure the blind is maintained for the patients and personnel mentioned previously. To maintain the blind, investigators will distribute blinded study drug treatment to patients as directed by the IWRS system. Investigators and patients will not be blinded to dose level, but will be blinded to treatment assignment (i.e., bardoxolone methyl vs. placebo).

An IWRS will manage treatment assignments and study drug dispensing. The only people with direct access to treatment assignments prior to database lock will be those individuals who develop and maintain the randomization code and the DSMB.

Following database lock after completion of each phase the study, randomization codes will be released to the statistical team for analysis.

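### The primary endpoint divides patients between scale categories 5 and 6, but the only clinical covariate named for the primary model divides them between 6 and 7; adding the missing split is a cheap efficiency gain of unknown, possibly negligible, size

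*Combined protocol and SAP*

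**What the plan says.** Section 4.2.2.1 counts a patient as recovered at Day 29 on this definition: "Proportion of subjects recovered (defined as alive, free of respiratory failure [e.g., need for non-invasive or invasive mechanical ventilation, high flow oxygen, or ECMO", plus freedom from renal replacement therapy. The scale in 4.2.2.2 puts "Hospitalized; oxygen by mask or nasal prongs" at category 5 and "Hospitalized; oxygen by NIV or High flow" at category 6.

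Randomisation (10.6.1, also 4.1) is stratified by "center and invasive mechanical ventilation (i.e., mechanical ventilation with endotracheal intubation) at baseline (yes or no". Section 10.4.2 bases the primary test on a "generalized linear model analysis accounting for the stratification factors of study center and mechanical ventilation status as covariates". It does not repeat the word invasive, but it calls this variable a stratification factor, so the intubation definition applies. The same section adds: "The primary efficacy endpoint will be a covariate-adjusted estimate as specified in the Statistical Analysis Plan".

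Section 5.1 admits patients on the strength of any one of several criteria, from "Radiographic infiltrates by imaging (chest x-ray, CT scan, etc" through supplemental oxygen and NIV to recent intubation. Section 5.2 excludes patients needing dialysis. The Schedule of Events lists a clinical status assessment at Screening and on Day 1, and the deterioration endpoint in 4.2.2.2 needs a baseline category in any case. Section 10.1 makes the formal SAP the final arbiter; that SAP is not in the file.

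**The concern.** The covariate and the endpoint cut the same scale in different places. Among non-intubated entrants, those in category 6 must leave a failure state to count as recovered, while those in categories 4-5 must avoid entering one. If these groups have different chances of being recovered at Day 29, baseline category explains outcome variation that the named model leaves in the error term.

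There is also a question of reading the result. One risk difference combines not getting worse (entry at 5 or below) with getting better (entry at 6 or above). The deterioration and mortality endpoints do not split the primary effect by baseline state, and the only subgroup the protocol names (10.4.8) is co-enrolled patients.

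**Working it through.** **1. The plan's own figure.** Inputs from 10.5: 50% versus 64%, two-sided 0.05, 400 patients 1:1, 2% drop-out, hence 200 × 0.98 = 196 per arm. With mean proportion 0.57:

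z = [0.14·√196 − 1.96·√(2 × 0.57 × 0.43)] / √(0.50 × 0.50 + 0.64 × 0.36) = (1.960 − 1.372) / 0.693 = 0.848, so power = 80.2%. The stated figure of about 80% reproduces.

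**2. Method.** For a risk difference (RD) standardised over baseline strata k with shares w, the large-sample variance is

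V = (1/196)·Σ w[p0(1−p0) + p1(1−p1)] + (1/392)·Σ w(RD_k − 0.14)²,

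and power = Φ(0.14/√V − 1.96). I compare two levels (not intubated / intubated) with three (5 or below / 6 / intubated).

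**3. Assumptions.** The documents give neither a baseline mix nor recovery by category. Everything in steps 4 and 5 is assumed: placebo recovery 50% overall, and one common odds ratio chosen to give 64% on drug.

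**4. Worked example.** Mix 60/25/15% (5 or below / 6 / intubated), placebo recovery 25% if intubated, and a 20-point gap between the first two groups. Placebo recovery is then 0.603 / 0.403 / 0.250 and drug recovery 0.739 / 0.557 / 0.383.

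- Two levels: the non-intubated stratum averages 0.544 and 0.685. The first sum is 0.394 + 0.064 = 0.458, V = 0.002335, power 82.6%.
- Three levels: 0.259 + 0.122 + 0.064 = 0.445, V = 0.002270, power 83.6%.
- Variance reduction: 1 − 0.002270/0.002335 = 2.8%. The same precision needs about 400 × 0.972 = 389 patients.

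The same mix at other gaps:

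| Placebo recovery gap, 5 or below minus 6 | Variance reduction | Power, two to three levels | Equivalent N |
|---|---|---|---|
| 0 points | 0% | no change | 400 |
| 10 | 0.7% | 82.6 to 82.8% | 397 |
| 20 | 2.8% | 82.6 to 83.6% | 389 |
| 30 | 6.5% | 82.5 to 84.9% | 374 |
| 40 | 11.8% | 82.5 to 86.9% | 353 |

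Across five mixes (category 6 at 10-40%, intubated at 10-20%), gaps of 20-30 points give +0.6 to +2.5 power points.

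**5. Wider grid.** Category 6 share 10-40%, intubated share 5-20%, recovery if intubated 12, 20 or 30%. Gain in information (V for two levels over V for three, minus 1): 0% at no gap, 0.3-0.9% at 10 points, 1.5-3.8% at 20, 3.6-9.0% at 30 and 6.9-17.2% at 40.

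**6. Simulation.** 3,000 trials of the step 4 mix at a 20-point gap, 20 centres, logistic model with standardisation. Power went from 84.2% to 84.8% without centre terms and from 84.8% to 85.0% with them. Type I error was 4.4% and 4.5% without centre terms, and 4.6% for both models with them.

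**7. Share of recoveries by entry state.** In the step 4 example, 0.60 × 0.603 / 0.50 = 72% of placebo patients counted as recovered entered at category 5 or below. This figure follows from the assumed mix and rates.

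**The case against.** The strongest reply is that nothing here is wrong. Adjusting for the stratification factors is standard, type I error is sound and the stated power holds. Section 10.4.2 hands the adjusted estimate to the SAP and 10.4.8 hands it the subgroups, so the SAP may already contain this split. All of that stands. The narrower point survives: 10.4.2 followed as written omits a baseline split that matches the endpoint and is already scheduled for collection.

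A reader might infer that the trial forgoes 15% or more of its information. The documents do not support that. Gains of 15-18% arise in assumed cases with a recovery gap above 40 points and 30-40% of patients in category 6.

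A reader might also infer that the endpoint is defective because category 4-5 entrants meet the listed criteria on arrival. It is measured at Day 29 and fails on death and renal replacement therapy as well, so entry state does not settle it. The list of failure states is given as examples, so a patient on a non-rebreather mask is arguable.

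The baseline value is less tidy than the schedule suggests. Visit 1 (7.2.2.1) lists dosing before clinical status, and screening may be up to three days old (7.2.1). Error in the baseline category would shrink the gain: in one assumed case with a 29.5-point gap, misclassifying 10% of category 6 and 5% of the lower group cuts it from 6.8% to 4.9%.

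**Conclusion.** The mismatch is real and follows from the text. It is an efficiency and reporting improvement to consider, with no error of validity. The documents do not support reading it as bias, as a shortfall in power or as a reason to change the randomisation strata; in every mix examined, the planned model already exceeds 80% power.

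The size rests wholly on an assumed placebo recovery gap and baseline mix: about nothing if category 6 patients recover like categories 4-5, roughly 1.5-4% more information at 20 points, 3.5-9% at 30, and more only near 40. Whether any precision is lost in the end depends on the SAP.

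**What to change.** In 10.4.2 and the SAP:

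- Keep centre and the intubation stratification factor in the primary model, and state that ventilation status there means the randomisation factor.
- Within the non-intubated stratum, add baseline category 6 versus 5 or below. Take it from the last clinical status assessment before randomisation, using the screening value if there is no Day 1 value from before randomisation.
- Report the standardised risk difference with its 95% confidence interval.
- State whether a non-rebreather mask counts as respiratory failure.
- Add the primary risk difference by baseline category 5 or below versus 6 or above as a prespecified descriptive subgroup.

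The cost is wording, one model parameter and one subgroup row. Randomisation, visits, data collection and sample size are unchanged. It must be settled before database lock and unblinding, when 10.1 requires the SAP to be final.

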### 4.2.2.2 Secondday Efficacy Endpoint (assessed at Day 29 unless stated otherwise)

- Number of renal replacement therapy (RRT)-free days
- Number of mechanical ventilation-free days
- All-cause mortality
- Proportion of subjects experiencing a deterioration from baseline (as defined by a 1-point worsening) to end of treatment or Day 29 (whichever comes first) in clinical status using an 11-category ordinal scale:
  - 0 – Uninfected; no viral RNA detected
  - 1 – Asymptomatic; viral RNA detected
  - 2 – Symptomatic; Independent
  - 3 – Symptomatic; assistance needed
  - 4 – Hospitalized; no oxygen therapy
  - 5 – Hospitalized; oxygen by mask or nasal prongs
  - 6 – Hospitalized; oxygen by NIV or High flow
  - 7 – Intubation & Mechanical ventilation;  $pO_2/FIO_2 \geq 150$  or  $SpO_2/FIO_2 \geq 200$
  - 8 – Mechanical ventilation  $pO_2/FIO_2 < 150$  ( $SpO_2/FIO_2 < 200$ ) or vasopressors
  - 9 – Mechanical ventilation  $pO_2/FIO_2 < 150$  and vasopressors, dialysis or ECMO
  - 10 – Death

### 4.2.2.3 Exploratory Efficacy Endpoint (assessed at Day 29 unless stated otherwise)

- Change from baseline in eGFR
- Time to recovery
- Recovery at Day 60
- Change from baseline in  $PaO_2/FiO_2$  (while hospitalized on Day 5, 8, 15, and end of treatment)
- Change from baseline in D-dimer, C-reactive protein (CRP), LDH, troponin and cytokine levels (while hospitalized on Day 5, 8, 15, and end of treatment)

## 5 Study Enrollment and Withdrawal

### 5.1 Inclusion Criteria

In order to be eligible to participate in this study, an individual must meet all of the following criteria:

1. Laboratory-confirmed COVID-19 infection as determined by polymerase chain reaction (PCR)
2. Hospitalized patients that meets one of the following conditions:
  - a. Radiographic infiltrates by imaging (chest x-ray, CT scan, etc.); OR

CONFIDENTIAL

This material is the property of the NYU School of Medicine and Langone Medical Center. Do not disclose or use except as authorized in writing by the study sponsor

- b. At rest, blood oxygen saturation  $\leq$  94%; OR
  - c. Require supplemental oxygen; OR
  - d. Requiring non-invasive ventilation; OR
  - e. Requiring invasive mechanical ventilation for up to 2 days.
3. Age  $\geq$  18 years. Enrollment of patients  $\geq$ 70 years of age may be limited (e.g., comprise no more than 10% of all randomized patients), pending safety review by the DSMB and executive committee
  4. Participant or legally authorized representative is willing to give informed consent

## **5.2 Exclusion Criteria**

An individual who meets any of the following criteria will be excluded from participation in this study:

1. Intubated and on invasive mechanical ventilation for three or more days at the time of randomization
2. Known left ventricular ejection fraction (LVEF)  $<$ 40% or prior hospitalization for heart failure
3. Cardiac arrest
4. Shock
5. Known uncontrolled bacterial, fungal, or non-COVID viral infection
6. eGFR  $<$ 30 ml/min/1.73 m^2 or requiring dialysis
7. ALT or AST  $>$  5X ULN
8. History of cirrhosis, chronic active hepatitis or severe hepatic disease
9. Pregnant or lactating women
10. Enrolled in other trial of unapproved therapies, unless approved by trial Principal Investigator. In general, co-enrollment will be permitted unless there are safety concerns, mechanistic incompatibility or inability to adjudicate serious adverse events and will be decided on a case by case basis.
11. If in the opinion of the clinical team, progression to death is imminent and inevitable within the next 24 hours, irrespective of the provision of treatments

## **5.3 Vulnerable Subjects**

The study will include subjects with diminished or lack of capacity to provide consent if their Legally Authorized Representative (LAR) is able to provide consent on their behalf. Due to the known progression of the COVID-19 disease, there is the possibility that a patient may be sedated, under mechanical ventilation, or under the effects of hypoxia, etc. that may contribute to an altered mental status before the study team is able to obtain written consent. We believe that this group of patients will have a potential for direct benefit by participating in the trial. In addition to the standard of care monitoring by their treatment team, there will be additional monitoring for the study. Overall, we believe that participation in this trial will facilitate close monitoring of their clinical status which may improve their clinical care.

As usual, assessment of a subject's capacity will be conducted by the treating physician based on the standard clinical assessment of capacity, which includes assessment of patients understanding of the facts presented, assessment of their appreciation and reasoning about the choice, etc. and communicated to the study team. If it is determined that the subject is unable to provide consent, consent will be obtained from subject's LAR before study-related procedures can begin. The study will be explained to the LAR by the study team using the IRB-approved Informed Consent Form. The hierarchy of identifying the LAR will be in the following order: health care agent, spouse (if not legally separated), domestic partner, adult child, parent, adult sibling, and close friend. The hierarchy may vary from state to state and the local site should refer to their local regulations. Identification and verification of the LAR will follow the standard policies and procedures in place at each study site.

### **CONFIDENTIAL**

This material is the property of the NYU School of Medicine and Langone Medical Center. Do not disclose or use except as authorized in writing by the study sponsor

Subjects' capacity will be re-assessed at each study visit with the treatment team. Once the participant regains capacity to consent, they will be informed of their participation in the study and will have an opportunity to withdraw from further participation in the study. Subjects who regain the capacity to consent and decline to continue participation will be asked if previously collected data can still be used. If they decline to allow use of previously collected data, their data will be discarded. If a subject provides consent with capacity, and subsequently loses capacity, their participation in the study is expected to continue unless the LAR notifies the study team of study withdrawal.

#### **5.4 Strategies for Recruitment and Retention**

Participants will be screened by designated qualified clinical staff in an electronic medical records system, such as EPIC or similar, using the inclusion and exclusion criteria specified for the study. When a potential participant is identified, the Investigator will contact the participant's treating physician (TP), or equivalent, to further verify eligibility for the study. The Investigator and TP will determine the best way to approach the potential participant to introduce the study. The consenting process will occur in an in-patient setting. In addition to screening by the study team, the Principal Investigator and Investigators at participating sites may publicize this study internally to clinical colleagues. Referrals from clinical colleagues will be reviewed to verify eligibility before proceeding to the consenting process.

#### **5.5 Duration of Study Participation**

Bardoxolone methyl or placebo will be administered for the duration of hospitalization (until recovery), for up to a maximum of 29 days. A final follow-up visit will occur 60 days after randomization. Total duration of study participation is estimated to be approximately 2 months.

#### **5.6 Total Number of Participants and Sites**

Recruitment will end when approximately 400-440 participants are enrolled. Recruitment is planned to occur at approximately 20 sites.

#### **5.7 Participant Treatment Discontinuation**

##### **5.7.1 Reasons for Treatment Discontinuation**

Study drug discontinuation refers to a patient's stopping administration of study drug. Participants are free to discontinue study treatment at any time for any reason without prejudice to their medical care. Furthermore, the investigator may discontinue a patient from study drug. The reason for a patient's discontinuation from study drug will be recorded in the electronic case report form (eCRF).

Reasons for study drug discontinuation may include the following:

- Adverse event;
- Death;
- Lost to follow-up;
- Physician decision;
- Protocol specified criterion met;
- Withdrawal by subject

Patients who are discontinued from study drug should still continue in the study, complete all study visits, and undergo all scheduled study assessments, if possible.

